**PROTOCOL SYNOPSIS**

Title	Cryospray Therapy for Benign Airway Stenosis: a pilot study
Short title	(pilot-CRYOSTASIS)
Study objective	
 
1. To assess the effectiveness of cryospray therapy used in addition to current standard of care endoscopic therapies in preventing short term recurrent airway stenosis.
 
2.
 

Study device	truFreeze Spray Cryotherapy System (US Endoscopy)
Design	, Multicenter, investigator-initiated, industry-funded, randomized 1:1, superiority study. The protocol allows for inclusion of an additional external site if recruitment is insufficient after 6 months for study.
Study Centers	Multicenter at academic and community hospitals
Number of subjects	40
Timeline	12-month recruitment, 6 months follow up
Inclusion criteria	
 
1. Referral to interventional pulmonology or otorhinolaryngology for endoscopic management of suspected benign tracheal stenosis.
 
2. Significant tracheal stenosis defined by stenosis <math>\geq 50\%</math> of tracheal lumen assessed on chest CT or clinical symptomatology warranting evaluation.
 
3. Able to provide informed consent.
 
4. Age <math>> 18</math>
 

Exclusion criteria	
 
1. Inability to provide informed consent.
 
2. Pregnancy
 
3. Known or suspected malignant central airway stenosis
 
4. Patient has already been enrolled in this study.
 
5. Study subject has any disease or condition that interferes with safe completion of the study including: 
 
a. Hypoxemia with need for supplemental oxygen <math>\geq 2\text{L/min}</math> by nasal canula
 
b. Pneumothorax in the previous 12 months
 
c. Severe COPD (defined as a <math>\text{FEV1/FVC} < 70\%</math> and <math>\text{FEV1} < 30\%</math> predicted) and/or severe persistent asthma.
 
d. Hemodynamic instability with systolic blood pressure <math>< 90</math> mmHg or heart rate <math>> 120</math> beats/min, unless deemed to be stable with these values by the attending physicians.
 
 
 
6. Prior complications with SCT (Spray cryotherapy)
 
7. Contraindication to rigid bronchoscopy
 
8. Significant tracheomalacia or alterations in cartilage integrity on CT (Computed Tomography) that would require stent placement or surgical referral.
 
9. Greater than 1 BCAS intervention, excluding cricotracheal resection, within 6 months before enrollment.
 

Primary endpoint	The degree of re-stenosis at 6 months, expressed as the percentage of airway lumen volume within

	the stenotic segment, at 6 months compared to personal best patency volume on CT scan performed within two weeks of the study intervention. If patients require repeat intervention before six months based on clinical course, a CT chest before this re-intervention will be analyzed for the primary outcome.
Secondary endpoint	
 
• Change in PEF (Secondary)
 
• Change in QOL questionnaire (Secondary)
 
• Incidence of complications between groups (Secondary)
 

Statistical methodology	We hypothesize the patency assessed at 6 months will be 90% of baseline in the intervention group and 70% in the control group, with SD 20% in the control group. A sample size of 16 subjects in control and 16 subjects in intervention group will have 80% power to detect an increase in stenotic volume of 20% from control arm with type I error of 0.05. Eight additional patients will be recruited to account for attrition and crossover. Study will be done using the intention-to-treat principle. Continuous and categorical variables will be analyzed using the appropriate methodology accounting for non-normal distributions. Patients will be blinded to intervention including those evaluating the volumetric CT's and those performing statistical analysis.

PEF: Peak expiratory flow

FEV1: Forced expiratory volume in one second

FVC: Forced vital capacity

6MWD: 6-minute walk distance

COPD: Chronic Obstructive Pulmonary Disease

CCQ: COPD Clinical Questionnaire

VUMC: Vanderbilt University Medical Center

ITS: Idiopathic tracheal stenosis

BMI: Body mass index

ROI: Region of interest

GSE: General safety events

SAE: Serious adverse events

eCRF: Electronic case report form

IRB: Institutional review board

HIPPA: Health Information Portability and Accountability Act

GCP: Good clinical practice

### **2.1 Investigate team and research environment**

Vanderbilt has a complex airway center including interventional pulmonology, otorhinolaryngology, and thoracic surgery.. The Vanderbilt University Institute of Imaging Science is a trans-institutional initiative within Vanderbilt University serving physicians, scientists, students, and corporate affiliates. Vanderbilt Institute for Clinical and Translational Research (VICTR) VICTR is Vanderbilt's virtual home for clinical and translational research. Supported by the Vanderbilt University Medical Center's Office of Research and the NIH sponsored Clinical and Translational Science Award (CTSA), the mission of the institute is to transform the way ideas and research discoveries make their way from origin to patient care. REDCap (Research Electronic Data Capture) is a secure web application for building and managing online surveys and databases. While REDCap can be used to collect virtually any type of data (FISMA (Federal Information Security Management Act), and HIPAA- compliant environments), it is specifically geared to support online or offline data capture for research studies and operations.

## 3. Statement of compliance

This human subject study will comply with all applicable federal, state, and local laws and regulations, including accepted standards of good clinical practice as adopted by current Food Drug Administration (FDA) regulations and statutes. Participating study sites shall only allow individuals who are appropriately trained and qualified to assist in the conduct of the study.

## 4. Purpose of the study

### **4.1: Overview**

Benign central airway stenoses (BCAS) are an important cause of pulmonary morbidity and mortality.

. Because of the Coronavirus-19 (COVID19) pandemic we anticipate a substantial increase in BCAS in the coming years primarily due to post intubation tracheal stenosis. There are two general options available for management of BCAS: surgical resection or endoscopic management. Surgery is the preferred definitive option; however, the first therapeutic attempt is typically endoscopic with surgery reserved for recurrence. In addition, many patients are not candidates for surgical resection due to comorbid conditions, anatomical characteristic such as length or complexity of stenosis. Symptomatic stenosis frequently recurs resulting in numerous airway procedures. For example, at our institution, we have been doing 3-4 balloon dilation procedures a week for BCAS. Procedures such as dilation, thermal ablative therapies, and stenting may result in additional airway injury due to disruption of extracellular matrix. Spray cryotherapy (SCT) is a novel FDA cleared technique which allows for Liquid nitrogen (LN2) to be delivered in a metered fashion via a 7F catheter used and studied extensively in the esophagus. The proposed advantage of SCT in the treatment of BCAS is the possibility to decellularize the tracheal mucosa, leaving the extracellular matrix intact, which may then serve as a scaffold for appropriate wound repair, shifting the abnormal wound response after conventional endoscopic management to a more normal healing process. Thus, SCT has the potential for long-lasting endoscopic management of BCAS and is used as part of routine clinical care by many physicians, but there is a relative paucity of peer-reviewed data, and no randomized controlled trial has been performed. Management decisions require adequate assessment of the position, extent, and severity of the obstructing or stenotic segment. This has historically been done with endoscopic measurements which are subjective, recurrent symptoms or abnormal pulmonary function tests which are universally a late finding in airway stenosis, typically occurring when the stenosis exceeds 70%.

#### **4.2: Hypothesis**

We hypothesize that the addition of SCT to standard endoscopic treatment of benign airway stenosis will result in decreased stenosis recurrence at 6 months as estimated by quantitative radiologic assessment of the stenotic volume.

#### **4.3: Aims and Objectives**

1. To assess the effectiveness of cryospray therapy used in addition to current standard of care endoscopic therapies in preventing short term recurrent airway stenosis with a multicentric outcome evaluation

## 5. Study Design

### **5.1 : General Study Design**

Subjects will be randomly allocated in a 1:1 fashion to intervention standard of care (SOC) + SCT and control (SOC) groups. Participants will be blinded to the use of SCT to prevent knowledge of their group assignment from biasing their subjective assessments. Adjudicators in the primary outcome measurements (quantitative CT) will be blinded to group assignment as well. Patient will be excluded who have received greater than 1 BCAS intervention within 6 months of enrollment. All operators will be experienced truFreeze users with proper passive venting training as defined by truFreeze protocol. All operators will have a minimum experience of 5 prior procedures.

#### **5.1.2 : Intervention group**

Patients with BCAS randomized to the intervention group will undergo conventional endoscopic treatment and SCT. The airway will be managed with a Dedo laryngoscope, rigid bronchoscope, or a laryngeal mask airway (LMA) per operator preference and lesion location. Airway pictures will be documented through our propriety bronchoscopy software. The truFreeze spray cryotherapy system will be used to apply liquid nitrogen spray through a flexible catheter passed through the working channel of a therapeutic bronchoscope or rigid laryngoscope. Typical dosimetry with passive venting without suction starts with up to 2 cycles with standard endoscopy, with one cycle after. Spray applications will be adjusted as needed based on the size and region being ablated for up to a 10 second spray time. Standard of care endoscopic management may include radial mucosal cuts using a thermal modality, and mechanical dilation.

#### **5.1.3 : Control group**

Patients randomized to the control group will undergo the same airway management and standard of care interventions without use of SCT before and after intervention.

#### **5.1.4 : Both groups**

Peak expiratory flow (PEF) as well as a quality of life (QOL) questionnaires will be obtained within 2 weeks before and 2 weeks after the procedure. A repeat thin-cut chest CT or neck to quantitatively estimate of the patency volume will be obtained within 5 weeks of the first procedure to establish personal best patency volume (baseline patency volume, see below). A final CT scan will be done at 6 months after the index study procedure to evaluate the degree of restenosis. A QOL questionnaire and check-in survey will be done at the at the 3-month. Patients will have a final QOL questionnaire at the 6-month mark. Patients will be doing continuous PEF measurements weekly throughout the study with a mobile application as mentioned below.

Throughout the follow up period if a patient meets one or both of the following criteria: 1) drop in peak flow to 30% of previous value 2) drop in dyspnea score by 30% then the investigators will review if the patient needs an early CT and possibly repeat bronchoscopy. If patients undergo a repeat procedure before the 6-month CT they will be analyzed in an early reintervention subgroup. These patients will be including in the final analysis as per intention-to-treat and thereafter followed as per follow-up procedures outlined in the protocol. Patients in the SCT group may get repeat SCT as per discretion of the proceduralist. Patients in the SOC will not be able to get SCT and may only have repeat dilation with laser radial cuts.

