**Secondary and exploratory endpoints:**

- **Change in PEF (Secondary)**
- **Change in QOL questionnaire (Secondary)**
- **Incidence of complications between groups (Secondary)**

8. Statistical Design

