**8.4: Analytical Plan**

Descriptive statistics including means, standard deviations, and ranges for continuous parameters, as well as percentages and frequencies for categorical parameters will be presented. Investigations for outliers and assumptions for statistical analysis, e.g., normality and homoscedasticity will be made. If necessary, data will be transformed using Box-Cox power transformation. Comparisons between groups, i.e. intervention vs control, will be made using either the t-test or Wilcoxon Rank Sum test for continuous variables (such as patency volume, visual analog scales) and Chi-square test for categorical variables (such as incidences of pneumothorax). Other than the primary end point of percentage change of patency volume at 6 month, we will apply linear regression to assess the 6-month patency volume difference between control and intervention groups with the adjustment of baseline patency volume. Patients will be analyzed according to the per protocol and intention to treat principle. For peak flows, COPD questionnaire, intermediary time points will be analyzed using mixed model analysis for repeated continuous variables starting from 2 weeks pre-procedure, 3 months and then to 6 months post procedure.

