### **8.5 Measurements:**

PEF, quality of life using the Clinical COPD CCQ. Incidence of complications (hypoxemia, bleeding, pneumothorax rate, barotrauma). Baseline characteristics (age, sex, body mass index (BMI), smoking status, underlying disease process). CT Chest without contrast with 3D quantitative reconstruction.

**Peak expiratory flow monitoring:** Evidence supports the use of PEF as a simple, efficient, and accessible way of monitoring progression of tracheal stenosis. PEF has previously been captured in clinical encounters as component of the decision-making algorithm for surgical intervention in tracheal stenosis patients. Mobile Device Software ‘App’ can robustly capture longitudinal patient reported outcome measures..

**CQS mobile computing group:** Established expert programmer and data scientist support dedicated to mobile application development and support. Prior work with the CQS team successfully created and deployed a mobile app (Airflo™) for tracheal stenosis patient PEF reporting. Leveraging a Research Electronic Data Capture (REDCap) foundation, mobile apps are built on open-source mobile computing "MyCap" infrastructure (<https://projectmycap.org/>). MyCap leverages REDCap, ResearchKit (Apple: iOS), and ResearchStack (Android) to capture patient reported outcome measures, and physiologic tasks (such as maximum phonation time, voice samples, and peak expiratory flow rate) using iOS and Android mobile devices. REDCap is used to define tasks/instruments/surveys to be completed by participants. MyCap translates REDCap task metadata into a structure compatible with ResearchKit and ResearchStack. When a project participant completes a task, MyCap converts the results into a format compatible with REDCap before synchronizing back to the REDCap project.

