## 10. Clinical COPD Questionnaire

Nouraei and colleagues successfully validated the Clinical Chronic Obstructive Pulmonary Disease Questionnaire in a group of patients with laryngotracheal stenosis. Total and domain-specific scores also corrected with FEV1 and PEFR. The authors found statistically significant differences between total and domain specific CCQ scores across populations of patients with different preoperative stenosis severities ( $P < 0.001$  in all cases; one-way analysis of variance). Furthermore, there were statistically significant differences between preoperative and postoperative total and domain-specific CCQ scores ( $P < 0.001$  in all cases; Student's t-test).

We plan to use this questionnaire at carefully selected timepoints throughout the study timeline to assess symptom improvement pre- and post-intervention.

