## 21. COPD Questionnaire (CCQ)

CLINICAL COPD QUESTIONNAIRE  Please circle the number of the response that best describes how you have been feeling during the past 7 days . (Only one response for each question).							
On average, during the past 7 days, how often did you feel:	never	hardly ever	a few times	several times	many times	a great many times	almost all the time
1. Short of breath while at rest ?	0	1	2	3	4	5	6
2. Short of breath while doing physical activities ?	0	1	2	3	4	5	6
3. Concerned about getting a cold or your breathing getting worse?	0	1	2	3	4	5	6
4. Depressed (down) because of your breathing problems?	0	1	2	3	4	5	6
In general, during the past 7 days, how much of the time:							
5. Did you cough ?	0	1	2	3	4	5	6
6. Did you produce sputum or phlegm (chest mucus)?	0	1	2	3	4	5	6
On average, during the past 7 days, how limited were you in these activities because of your breathing problems:	not limited at all	very slightly limited	slightly limited	moderately limited	very limited	extremely limited	totally limited / or unable to do
7. Strenuous physical activities (such as climbing stairs, hurrying, participating in sports)?	0	1	2	3	4	5	6
8. Moderate physical activities (such as walking, housework, carrying things)?	0	1	2	3	4	5	6
9. Daily activities at home (such as dressing, washing yourself)?	0	1	2	3	4	5	6
10. Social activities (such as talking, being with children, visiting friends/relatives)?	0	1	2	3	4	5	6

© The CCQ is copyrighted. It may not be altered, sold (paper or electronic), translated or adapted for another medium without the permission of T. van der Molen, Dept. of General Practice, University Medical Center Groningen, [name].

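### The post-procedure CCQ has no earliest day but a 7-day recall, so a form completed in the first six days partly reports pre-procedure symptoms

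*Protocol*

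**What the plan says.** Section 5.1.4 of the protocol schedules the early assessments for both groups: peak expiratory flow and quality-of-life "questionnaires will be obtained within 2 weeks before and 2 weeks after the procedure". Further questionnaires follow at 3 months and at the end: "Patients will have a final QOL questionnaire at the 6-month mark". The assessment table in Section 20 has a post-procedure column for questionnaire delivery but gives no day.

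Section 8.5 names the instrument: "quality of life using the Clinical COPD CCQ". The form printed in Section 21 opens its first block with "On average, during the past 7 days, how often did you feel", and the other two item blocks use the same 7-day period, so all ten items share it.

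Section 10 gives the purpose: "We plan to use this questionnaire at carefully selected timepoints throughout the study timeline to assess symptom improvement pre- and post-intervention". Section 7 lists change in the quality-of-life questionnaire as a secondary endpoint without saying between which time points. Section 8.4 puts the questionnaire into a mixed model, "starting from 2 weeks pre-procedure, 3 months and then to 6 months post procedure".

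**The concern.** The window and the recall period do not fit together. A patient who completes the CCQ two days after the procedure has followed the protocol, yet five of the seven days asked about came before treatment. That form is a blend of the two periods and not the post-intervention score that Section 10 wants.

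The problem is one-sided. A form completed before the procedure can only look back on pre-procedure days, so only the post-procedure score is mixed. If symptoms improve, the mixture always shrinks the early change.

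At stake is the only CCQ measurement scheduled close to the treatment, in a pilot of 40 patients meant to inform larger studies. Delivery timing is a matter for the protocol. Once a form has been completed on days 1 to 6, no later analysis can separate the days before the procedure from those after it.

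**Working it through.** The protocol states no figure on this point, so there is none to reproduce. The check compares two time windows.

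**Inputs from the protocol**
- Post-procedure window: up to 14 days, no earliest day (Section 5.1.4).
- Recall period: 7 days for all items (Section 21).

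**Assumptions, not in the protocol**
- The procedure falls on day 0 and forms are completed on day 1 or later.
- Patients weight the seven recall days equally.
- For the averages only, completion is spread evenly over the stated days.

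**Step 1: overlap by day.** The share of recall lying before the procedure is f(d) = max(0, 7 − d)/7.

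| Day completed | f(d) |
|---|---|
| 1 | 6/7 = 86% |
| 2 | 5/7 = 71% |
| 3 | 4/7 = 57% |
| 4 | 3/7 = 43% |
| 5 | 2/7 = 29% |
| 6 | 1/7 = 14% |
| 7 to 14 | 0% |

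Six of the 14 days overlap (6/14 = 43% of days, which is not a share of patients).

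**Step 2: average overlap.** The sum over days 1 to 6 is (6 + 5 + 4 + 3 + 2 + 1)/7 = 21/7 = 3.
- Even completion over days 1 to 14: 3/14 = 21%.
- All forms on days 1 to 6, evenly: 3/6 = 50%.
- All forms on day 7 or later: 0%.

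**Step 3: effect on the early change.** Let B be a patient's true score before the procedure and A the true score after it. The observed post-procedure score is f·B + (1 − f)·A, so the observed improvement is (1 − f)·(B − A). The early improvement is understated by the fraction f: 86% at worst (day 1), 21% on average with even completion over days 1 to 14, and nothing from day 7.

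**Step 4: effect on the comparison of arms.** Randomisation makes the expected B equal in the two arms, and the window is the same in both. With the same spread of completion days, unrelated to how much a patient improves, the expected early difference is (1 − mean f) times the true one. It moves towards zero and does not change sign.

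**Step 5: noise.** Under even completion over days 1 to 14, the mean of f² is (36 + 25 + 16 + 9 + 4 + 1)/49/14 = 91/686 = 0.133. The variance of f is 0.133 − 0.214² = 0.087, so its standard deviation is about 0.29. For patients with the same true improvement, the choice of completion day alone spreads the observed improvement with a standard deviation of about 0.29 times that improvement.

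**Step 6: after the change.** With completion limited to days 7 to 14, f = 0 on every allowed day.

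**The case against.** The strongest reply is that the protocol does not name the early score in its longitudinal analysis. Section 8.4 starts from the pre-procedure score and goes on to 3 and 6 months, and Section 7 does not tie the secondary endpoint to the early form. The 3- and 6-month scores are well clear of the index procedure. This stands and limits the reach of the point. It does not remove it, because the form is scheduled for every patient and Section 10 gives a pre-to-post purpose that the early score would naturally serve.

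A second reply is that the sentence may mean a visit at two weeks. Section 8.4 does turn the pre-procedure window into a nominal 2-week time point. On that reading there is no overlap. It is the less natural reading of Section 5.1.4, and stating an earliest day would settle the matter.

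Third, the size depends on when patients complete the form and how they weight the recall days, and the protocol gives neither. If most forms arrive near two weeks, the effect is close to nil. This is right, and the averages above should be read as illustrations. The day-by-day overlap is calendar arithmetic and does not depend on when patients actually respond.

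Some stronger readings are tempting but unsupported:
- A reader might infer a bias for or against spray cryotherapy. Participants are blinded and both arms share the window, so dilution and noise are expected, not an advantage to one arm. A within-patient improvement after a procedure that both arms undergo is also not the benefit of adding cryotherapy.
- A reader might infer that the early CCQ sets a best symptom level, so that later worsening is hidden. The protocol defines a personal best only for CT patency volume. The dyspnoea score that triggers early review has no stated reference value and is not identified as the CCQ.
- A reader might extend the point to repeat procedures. No separate CCQ is scheduled after one.

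**Conclusion.** The point holds as a modest design flaw confined to the early post-procedure CCQ score. On the natural reading of Section 5.1.4, forms completed on days 1 to 6 comply with the protocol but draw 86% down to 14% of their recall from before treatment. If symptoms improve after the procedure and recall days count equally, the early improvement is understated by the same share: about 21% on average with even completion over days 1 to 14, within a range from 0% (all forms from day 7) to 86% (all on day 1). Any early difference between arms shrinks in proportion, given similar completion timing in both arms.

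The CT primary endpoint and the 3- and 6-month CCQ scores are untouched. The protocol therefore does not support a claim that its named longitudinal CCQ analysis is compromised. The change is worth making because it is cheap and the lost information cannot be recovered afterwards.

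**What to change.** In Section 5.1.4 and the questionnaire row of the Section 20 table, state that the post-procedure CCQ is completed on days 7 to 14 after the index procedure. Set the release date in REDCap or MyCap to match. Peak flow has no recall period and needs no change on this account.

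The cost is one line of protocol text, one table entry and a delivery setting, with no extra visit. The downside is a completion window about a week shorter, which leaves less time for reminders. The rule should not be extended to repeat procedures: no separate CCQ is scheduled there, and it could push a 3- or 6-month form off its date.

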**Primary endpoint:**

The primary endpoint will be the degree of re-stenosis at 6 months expressed as the percentage of airway lumen volume within the stenotic segment at 6 months compared to personal best patency volume on CT scan performed within five weeks of the study intervention. If patients require repeat intervention before six months based on clinical course, a CT chest before this re-intervention will be analyzed for the primary outcome. All analyses will be performed using OsiriX (Pixmeo, Geneva, Switzerland, see below).

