Deanonimized DICOM images will be transferred and analyzed using the OsiriX (Pixmeo, Geneva, Switzerland) threshold-based region growing algorithm function for volume segmentation. Briefly, the process is as follows: The operator identifies proximal and distal ends of the tracheal stenotic and use the region of interest (ROI) function to segment the trachea in 3 to 4 different areas spanning the length of the stenotic segment using the closed polygonal function (Figure 5). The ROI volume function will then be used to generate missing intervening ROIs and the repulsor function will be used to manually adjust the boundaries of the ROI. The volume of the final airway will then be computed and a three-dimensional image saved for documentation (Figure 6).

To classify the degree of tracheal stenosis, we will manually annotate the trachea (wall, stenosis, and patency) on all scans. Expert manual review will be performed by one of two experienced investigators ([name]) In an exploratory analysis to enable routine automated analysis of stenotic volumes, we will perform transfer learning using our abdomen/thoracic model using leave-one-out cross-validation. Mixture modeling with image intensity classification will be used to separate the tracheal wall, stenosis region, and patency following our work in the abdomen.

[figure not shown]

Figure 5. Closed polygonal function-derived 2D-tracheal segmentation

[figure not shown]

Figure 6. 3D reconstruction and computation of the patency volume

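### The CT scans that form the primary-endpoint ratio are specified inconsistently, so a patient's baseline and endpoint scans need not match in body region or slice thickness

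*Protocol*

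**What the plan says.** Section 7 of the protocol defines the primary endpoint as "the percentage of airway lumen volume within the stenotic segment at 6 months compared to personal best patency volume". It is therefore a within-patient ratio of two CT volumes. The protocol describes the scans behind that ratio in several places:

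- **Personal-best scan (denominator), Section 5.1.4:** "A repeat thin-cut chest CT or neck to quantitatively estimate of the patency volume".
- **6-month scan (usual numerator), Section 5.1.4:** "A final CT scan will be done at 6 months after the index study procedure to evaluate the degree of restenosis". No body region or slice thickness is given.
- **Scan before early re-intervention (numerator for those patients), Section 7 and the synopsis:** "a CT chest before this re-intervention will be analyzed for the primary outcome". No slice thickness is given.
- **Section 8.5, with no limit by visit:** "CT Chest without contrast with 3D quantitative reconstruction".
- **Study Assessment Table (Section 20):** one CT row, labelled chest, covering the post-procedure and 6-month visits.

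The neck option and the thin-cut requirement each appear once, both for the personal-best scan. Section 9.1 describes the volume measurement in detail but does not require a patient's scans to match in region, slice thickness or reconstruction.

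**The concern.** A ratio of two volumes from the same patient is a sound endpoint when both volumes are measured in the same way, because a shared measurement error largely cancels. When the two scans differ in kind, the error does not cancel and cannot be told apart from a change in the airway.

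Section 9.1 leaves room for such an error. Volume comes from a "threshold-based region growing algorithm function for volume segmentation" with manual adjustment, and "The operator identifies proximal and distal ends of the tracheal stenotic". Both steps work on whatever slices and coverage the scan provides.

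A neck baseline scan is a realistic case. The protocol itself offers it, takes referrals from ENT, and lets lesion location guide the choice of airway instrument (Section 5.1.2). If such a patient needs early re-intervention, Section 7 makes a chest CT the endpoint scan. At stake are the precision of the primary comparison, the meaning of the absolute patency percentages that are to inform later studies, and the endpoint itself in any patient whose segment is not fully covered. An analysis plan cannot repair scans that were acquired differently.

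**Working it through.** **1. The scan rules side by side**

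| Scan | Role in ratio | Region | Slice requirement |
|---|---|---|---|
| Personal best (5.1.4) | denominator | chest or neck | thin-cut |
| 6 months (5.1.4) | numerator | not stated | not stated |
| Before early re-intervention (7, synopsis) | numerator | chest | not stated |
| Any (8.5) | both | chest | not stated |
| Post-procedure and 6 months (Section 20 table) | both | chest | not stated |

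Two things follow. The neck option in 5.1.4 conflicts with 8.5 and the table. Also, a neck denominator with a chest numerator is permitted at 6 months, and for early re-intervention it is what the text literally produces.

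**2. How a mismatch enters the endpoint**

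Let the true ratio be R, and let the two scans carry proportional errors e0 (baseline) and e1 (endpoint). The observed ratio is R × (1 + e1)/(1 + e0). With like-for-like scans e1 is close to e0 and the factor is close to 1. With unlike scans it can fall on either side of 1, so a mismatch can mimic re-stenosis or hide it.

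**3. The plan's own sample size**

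Inputs from Section 8.3: 90% against 70% of baseline (difference 20 points), SD 20 in the control arm, type I error 0.05, two-sample t-test, 16 per arm, 80% power. Assumed here: a two-sided test and the same SD in both arms.

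- Normal approximation: n = 2 × (1.960 + 0.842)² × 20²/20² = 15.7, so 16 per arm. Power at 16 per arm is 0.807.
- Noncentral t: noncentrality 20/(20 × √(2/16)) = 2.83, 30 degrees of freedom, power 0.781.

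The stated figure is reproduced and is not in dispute.

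**4. Illustration of added noise**

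The documents give no scan-to-scan error, so the extra SD is an assumption and is shown as a range. It is taken as independent, equal in both arms and not already contained in the planned SD of 20. Total SD = √(20² + extra²).

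| Extra SD (points) | Total SD | Power, 16 per arm (noncentral t) | Power, 20 per arm |
|---|---|---|---|
| 0 | 20.0 | 0.781 | 0.869 |
| 5 | 20.6 | 0.757 | 0.848 |
| 10 | 22.4 | 0.687 | 0.787 |
| 15 | 25.0 | 0.591 | 0.693 |

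The last column applies if all 40 enrolled patients yield an endpoint.

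**5. Illustration of a common shift**

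Suppose every endpoint volume were scaled by the same factor in both arms, from −10% to +10% (again an assumption). The planned 90 against 70 would become 81 against 63 at one end and 99 against 77 at the other. The difference moves only from 20 to between 18 and 22 points, while the absolute patency values move by 7 to 9 points.

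**The case against.** The strongest reply is that the protocol mainly describes matched chest scans. Section 8.5, the assessment table and the re-intervention rule all say chest, and the one departure is an ungrammatical phrase in 5.1.4. The 6-month scan, mentioned in the next sentence, can be read as the last of the same series. Silence on slice thickness is weaker than a contradiction, and an imaging manual or order template might settle it. This stands in part: the documents permit a mismatch at 6 months rather than prescribe one. But no manual is cited, and the neck option is an explicit permission that the chest-only passages contradict. A patient with a neck baseline scan and early re-intervention meets the conflict directly.

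Three stronger readings are tempting, and the documents do not support them.

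- **Scan differences count systematically as re-stenosis, or favour one arm.** The error can go either way. Allocation is randomised (Section 8.2) and CT readers are blinded to arm (Section 5.1), so it should be mostly similar between arms.
- **The table's labels show different acquisition protocols.** It marks the post-procedure scan as non-standard-of-care and the 6-month scan as standard of care. Those labels sit beside items such as IRB cost and statistician, and Section 14 ties standard of care to who pays. They do not say how a scan is acquired.
- **The power loss is known.** It is not. The documents give neither the size of a mismatch error nor the share of patients affected, nor the proportion of high lesions. They also do not say whether the planned SD already includes measurement error. If it does, adding more would count it twice.

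**Conclusion.** The point holds as an inconsistency in how the primary-endpoint scans are specified. As written, one patient's ratio may compare a thin-cut neck scan with a chest scan of unspecified slice thickness, and nothing in the protocol requires like-for-like scans.

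The expected consequence is added noise, distorted absolute patency values and possibly some lost endpoints. Bias between arms would need scan type to differ by arm. Unequal early re-intervention is one route, since that rule fixes a chest CT and the trial's hypothesis is that recurrence differs. Neither the direction nor the size of such a bias can be derived from the documents.

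The fall in power from 0.78 to between 0.76 and 0.59 is illustrative and rests wholly on the assumed extra SD of 5 to 15 points. That a chest scan could miss part of a high segment is likewise a possibility, not something the documents state. This is a cheap improvement, not a flaw that invalidates the design.

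**What to change.** Reconcile the synopsis endpoint, Sections 5.1.4, 7 and 8.5 and the assessment table around one rule: each patient's personal-best, 6-month and pre-re-intervention scans use the same body region and the same thin-slice reconstruction. The region, chest or neck, is set at the first scan so that it covers the stenotic segment. In the synopsis and Section 7, where the text now reads "a CT chest before this re-intervention will be analyzed for the primary outcome", refer instead to a CT by the patient's baseline scan protocol.

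The cost is a few lines of text and a CT order template, with no extra scans. The small downside is that scans billed as standard of care must be ordered to the study template, so the sponsor should check that this does not change who pays.
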